3.2.2 Secondary Objectives

1. To determine the safety and tolerability of the implantation of the RENCA cancer-cell-containing macrobeads in advanced pancreatic cancer subjects with respect to:
 - The peritoneum: irritation, inflammation, mechanical effects (over a period of at least 3 months);
 - Other intraperitoneal organs (liver, spleen, large and small intestines, kidney, bladder, omentum, etc.);
 - Local and systemic immune response (T and B cell/cellular, antibody responses);
 - Bacterial, viral zoonotic infection (clinical and hematological examination; PCR DNA analysis for viral DNA; specific viral antibodies);
 - Hypersensitivity reactions to murine antigens.
2. To determine progression, defined as the time from the first implantation until the first occurrence of any of the following events
 - a. Death due to any cause, or
 - b. Progression as defined by the presence of the occurrence of any three of the five following events:
 - i. An increase in the levels of tumor markers (e.g., CEA, CA19-9) of 50% from baseline determinations
 - ii. Radiographic progression including increase in primary or metastatic tumor size/volume; increasing metabolic activity of the presenting tumor or of new metastatic lesions on a PET/CT scan after the administration of radio-labeled fluorodeoxyglucose (FDG); and evidence of new metastatic lesions.

- iii. A decrease in the EORTC QLQ-C30 quality of life scale as compared to baseline of more than 25%;
(Above data will also be analyzed with censorship of deaths to further evaluate progression)
3. Determine overall survival (OS)
4. Circulating tumor cells will also be measured

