1 ADMINISTRATIVE STRUCTURE

This study is being conducted under the sponsorship of The Rogosin Institute (“the Sponsor”). The clinical monitoring, data management and statistical analyses of safety and efficacy are being performed under contract with Vital Systems, Inc. (VSI), in collaboration with the Sponsor.

This SAP supersedes any statistical considerations identified in the study protocol. Any differences between this statistical analysis plan and the study protocol will be presented and explained in the CSR.

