10.2 Statistical Analysis Methods

- All statistical testing will be considered strictly exploratory as the study was not powered based on statistical considerations.
- Exact 95% CIs will be calculated for rates.
- Survival analysis methods will be used analyze time-to-event outcomes; for non-mortality outcomes, the term “survival” will still be used to describe non-occurrence of the event being analyzed. Kaplan-Meier plots with 95% CIs will be generated to show probability of survival as a function of time since implantation. In addition, Kaplan-Meier estimates of the median survival time will be reported.
- The relationship between times from diagnosis of Stage IV disease diagnosis to the primary analysis time of origin and primary analysis time of origin to death will be examined (if feasible) using Cox regression model and Kaplan-Meier curves.
- The relationship between time-to-event outcomes and tumor markers (and other covariates, if feasible) will be assessed using Cox regression. Kaplan-Meier plots will be produced for descriptive assessment.
- Survival comparisons by implantation number will be performed, if feasible.
- Other explorations of efficacy data may be performed (if feasible), such as:
 - Testing for effects of baseline values of tumor markers and presenting stratified descriptive statistics, if deemed appropriate.
 - Plotting chronological subject profiles of specific parameters; i.e., plotting a set of parameters over time on the same graph for a given subject.

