16 APPENDICES

16.1 Listings

Listing #	Listings
16.2.1.1	Subject disposition
16.2.1.2.1	Subject progress through study, 1 st implant
16.2.1.2.2	Subject progress through study, 2 nd implant
16.2.1.2.3	Subject progress through study, 3 rd implant
16.2.1.2.4	Subject progress through study, 4 th implant
16.2.2.1	Inclusion
16.2.2.2	Exclusion
16.2.3	Eligibility
16.2.4.1	Baseline characteristics
16.2.4.2	Contraception methods
16.2.4.3	Medical history
16.2.4.4.1	Primary oncology diagnosis
16.2.4.4.2	Previous oncology diagnosis
16.2.4.7.1	Pre-treatment medications
16.2.4.7.2	Con meds
16.2.5	Implantation
16.2.6.1.1	Global Clinical Assessment
16.2.6.1.2	Activities of Daily Living
16.2.6.1.3	Quality of Life Scale
16.2.6.1.4	Pain Scale Assessment
16.2.6.1.5	ECOG
16.2.6.2.1	Tumor markers
16.2.6.2.2	Cytokines
16.2.6.3	Tumor size and state
16.2.6.4.1	Overall survival (from T ₀)
16.2.6.4.2	Time from first implantation to radiologically evident disease progression
16.2.6.5.1.1	Time from first implantation to death
16.2.6.5.1.2	Time from diagnosis of Stage IV disease to death
16.2.7.1.1	AEs
16.2.7.1.2	AE comments

Listing #	Listings
16.2.7.2	SAEs
16.2.7.3.1	Treatment-emergent AEs resulting in discontinuation
16.2.7.3.2	Treatment-emergent AEs resulting in death
16.2.8.1	Laboratory testing data collection
16.2.8.2.1.1	Serum chemistry toxicity grades
16.2.8.2.1.2	Serum chemistry
16.2.8.2.2.1	Hematology toxicity grades
16.2.8.2.2.2	Hematology
16.2.8.2.3.1	Immunophenotyping toxicity grades
16.2.8.2.3.2	Immunophenotyping
16.2.8.2.X	Other labs
16.2.8.3	Comments
16.2.8.4	Labs reported as AEs and/or with toxicity Grade ≥ 3
16.2.9.1	Physical exam
16.2.9.2	Neuro exam details
16.2.9.3	Visit reviews
16.2.9.4.1	Vital signs
16.2.9.4.2	Home care log vital signs
16.2.9.5	ECG
16.2.9.6	Wound check
16.2.9.7	Mouse antigen skin tests
16.2.9.8	Murine virus
16.2.9.9.1	Chest x-ray
16.2.9.9.2	CT / PET / MRI scans
16.2.9.9.3	Rad disease assessments done
16.2.9.10	Hospitalizations
16.2.9.11	Comments
16.2.9.12	PI signatures

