16.3 Figures

Figure #	Figure
14.2.1.1.1.1	Progression-Free Survival: any death
14.2.1.1.1.2	Progression-Free Survival: cancer-related death
14.2.1.1.X	Progression-Free Survival by Stratifier X
14.2.1.2.1	Overall Survival
14.2.1.2.X	Overall Survival by Stratifier X
14.2.1.3.1	Radiographically-evident PFS
14.2.1.3.X	Radiographically-evident PFS by Stratifier X
14.2.2.1.1	CA125, colorectal
14.2.2.1.2	CA125, pancreatic
14.2.2.2.1	Tumor markers, CA 19-9, colorectal
14.2.2.2.2	Tumor markers, CA 19-9, colorectal
14.2.2.3.1	Tumor markers, CEA, colorectal
14.2.2.3.2	Tumor markers, CEA, pancreatic
14.2.3.1.1	Chemistry, C-reactive protein, colorectal
14.2.3.1.2	Chemistry, C-reactive protein, pancreatic
14.2.4.1.1	Hematology, Sedimentation rate, colorectal
14.2.4.1.2	Hematology, Sedimentation rate, pancreatic

End of Analysis Plan

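### Pancreatic cohort: the added progression analysis censors deaths and only Kaplan-Meier is planned, so if read as a probability of progression it will be too high

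*Protocol*

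**What the plan says.** Protocol 3.2.2, which covers the pancreatic cohort only, times progression from first implantation to the first of two kinds of event. One is given as "Death due to any cause, or"; the other is progression, met by "any three of the five following events", although only three are listed. A further analysis of the same data follows: "Above data will also be analyzed with censorship of deaths to further evaluate progression".

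SAP 10.2 sets the method for time-to-event outcomes: "Kaplan-Meier plots with 95% CIs will be generated to show probability of survival as a function of time since implantation". It adds that survival will mean non-occurrence of the event even when that event is not death. Cox regression is planned for covariates. Neither document names cumulative incidence or any other competing-risk method.

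SAP 16.3 lists two progression-free survival (PFS) figures, "Progression-Free Survival: any death" (14.2.1.1.1.1) and "Progression-Free Survival: cancer-related death" (14.2.1.1.1.2). SAP 16.1 lists "Time from first implantation to radiologically evident disease progression" without saying how deaths are handled. The SAP outcome lists (3.3.1 and 10) contain neither PFS nor time to progression. SAP 1 states: "This SAP supersedes any statistical considerations identified in the study protocol".

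**The concern.** Kaplan-Meier treats a censored subject as still able to have the event later, at the same rate as those who remain under observation. That is reasonable for a subject still alive at the data cut. It is not reasonable for a subject who has died. The estimator in effect passes the dead subject's share on to those still at risk, some of whom then progress. The complement of the curve answers how many would progress if nobody could die first, which is not the proportion of treated patients who progress. Because SAP 10.2 presents these curves as probabilities, the higher number is likely to be read as that proportion.

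This matters because the trial only estimates. Protocol Appendix 3 (item 1) gives the purpose as estimating parameters for planning later trials, and item 9 names progression estimates as part of the original sample size reasoning. An inflated progression probability could be carried into the event-rate assumptions of a later pancreatic protocol.

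**Working it through.** The documents state no progression rate, PFS rate or rate of death without progression, so there is no figure of the plan's own to reproduce. The calculation below illustrates size only.

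**Assumptions (not from the documents).** Constant hazards: *a* for progression and *b* for death without progression. Composite median 3 or 6 months. Share of first events that are deaths without progression: s = b/(a+b), from 10% to 75%.

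**Formulas.**
- Composite by time t: 1 − exp(−(a+b)t)
- One minus Kaplan-Meier, deaths censored: 1 − exp(−at)
- Cumulative incidence of progression: [a/(a+b)] × [1 − exp(−(a+b)t)]

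**Worked case, median 3 months, t = 6 months.** Here a+b = ln 2 / 3 = 0.231 per month, and exp(−0.231 × 6) = 0.25, so the composite is 75%. The other two become 1 − 0.25^(1−s) and (1−s) × 0.75. For s = 50% these are 1 − 0.25^0.5 = 50.0% and 0.5 × 0.75 = 37.5%. For s = 10% they are 1 − 0.25^0.9 = 71.3% and 0.9 × 0.75 = 67.5%.

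| Composite median | Time | s | 1 − KM | Cumulative incidence | Excess (points) |
|---|---|---|---|---|---|
| 3 mo | 6 mo | 10% | 71.3% | 67.5% | 3.8 |
| 3 mo | 6 mo | 25% | 64.6% | 56.2% | 8.4 |
| 3 mo | 6 mo | 50% | 50.0% | 37.5% | 12.5 |
| 3 mo | 6 mo | 75% | 29.3% | 18.7% | 10.5 |
| 3 mo | 12 mo | 10% | 91.8% | 84.4% | 7.4 |
| 3 mo | 12 mo | 50% | 75.0% | 46.9% | 28.1 |
| 6 mo | 6 mo | 10% | 46.4% | 45.0% | 1.4 |
| 6 mo | 12 mo | 50% | 50.0% | 37.5% | 12.5 |

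Over the whole grid the excess runs from about 1 to 28 points. A simulation with 40 subjects (the pancreatic number in Protocol Appendix 3, item 9), 4000 runs, s = 50% and median 3 months gave 50.1% by Kaplan-Meier and 37.5% by Aalen-Johansen at 6 months, in line with the closed form.

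**The cancer-death PFS figure.** The SAP gives a title only. Suppose the events are progression or cancer-related death, other deaths are censored, and other deaths are 2% to 20% of first events (assumed). With a composite median of 3 months, the 6-month event-free proportion reads 0.25^0.98 = 25.7% to 0.25^0.80 = 33.0%, against 25.0% in the any-death figure. The median reads 3/0.98 = 3.06 to 3/0.80 = 3.75 months, against 3.00. The curve therefore looks better than the any-death curve. Its complement still exceeds the cumulative incidence of progression or cancer-related death: 74.3% against 0.98 × 75% = 73.5%, and 67.0% against 0.80 × 75% = 60.0%.

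**The case against.** The strongest reply is that the safeguard is already in place. The main definition counts every death, an any-death PFS figure is listed, and the death-censored analysis is an addition. Shown beside the composite and labelled cause-specific, such an analysis is legitimate; it misleads only when read as an absolute risk. Everything is exploratory, with no formal test. With 40 subjects the 95% half-width for a proportion near 50% is 1.96 × √(0.25/40) = 15.5 points, which exceeds the bias in many of the cases above. Because the SAP overrides protocol statistics and does not define PFS in its text, it is also unclear whether the death-censored analysis will be run at all.

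Most of this stands, and it makes the point a small one. It does not remove it: SAP 10.2 labels its curves as probabilities and offers no alternative estimator, and imprecision does not excuse an error of known direction.

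Three stronger readings are tempting but unsupported.
- A reader might infer that many subjects die without progressing. The documents do not say so. Protocol section 2 says most patients with advanced pancreatic cancer die within a year, not that they die before progression. A minimum life expectancy of 6 weeks, a first scheduled post-implant PET-CT at Day 90 and a rule needing three events when only three are listed make it plausible, but it remains an assumption.
- A reader might infer that the cancer-death PFS figure also overstates failure. Against the any-death curve it does the opposite, and its event rule is undefined.
- A reader might infer that the colorectal analysis or a primary endpoint is affected. The censoring sentence sits in the pancreatic secondary objectives only.

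**Conclusion.** The point holds as a minor one, for a supplementary analysis in the pancreatic cohort. The direction is certain: with deaths censored, one minus Kaplan-Meier cannot fall below the cumulative incidence of progression. The size is not known from the documents. On the assumptions stated, with a composite median of 3 months, the 6-month excess is about 4 points at a 10% share of deaths without progression and 12.5 points at 50%. It is smaller with slower events and larger at 12 months. The cancer-death PFS figure is a separate gap in definition: if other deaths are censored, it flatters PFS relative to the any-death figure, and neither document gives a rule for attributing cause of death in this open-label trial. The primary endpoints, all-cause mortality for colorectal cancer and response rate for pancreatic cancer under the protocol, do not depend on either output.

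**What to change.** State the following in the SAP, since it takes precedence.

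1. Keep progression or death from any cause as the main PFS analysis, as already planned, and define it in the SAP text. The progression rule should be reconciled at the same time, because it refers to five events and lists three.
2. Report progression alone as a cumulative incidence (Aalen-Johansen), with death without progression as the competing event.
3. If a death-censored Kaplan-Meier curve is kept, label it cause-specific and say that its complement is not the probability of progression.
4. For Figure 14.2.1.1.1.2, either show the cumulative incidence of progression or cancer-related death with other death competing, and state how cause of death is assigned, or drop the figure. Replacing it with cancer-specific mortality would not do, because progression would then no longer be part of the endpoint.

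The cost is a few lines of SAP wording and standard software output. The curves use dates of progression and death that the planned analyses already need; only the cause-of-death rule in item 4 is new.

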3.2.3 Exploratory objectives

An addition to the endpoints for assessing efficacy will be, where possible, when a biopsy is indicated, a careful search for, and identification of, the niches of cancer stem and other cells within the niche bodies of the tumors the macrobeads are being used to treat. Markers of the niche used to identify these cells and study their properties (numbers, integrity of surrounding blood vessels, degree of stress) will include HLA, CD44+, CD133+.

3.3 Rationale for Study Dosages

Based on the animal studies conducted to date, as well as the Phase I human trial that has been completed to date, a reasonable dosage range (number of beads to be implanted) is 8 macrobeads per kilogram of body weight. We know that 16 macrobeads per kilogram were also well-tolerated in the Phase I human trial, but, at least with a single dose, this number was not seen to be any more effective than 8 macrobeads per kilogram. As it is planned to carry out up to four implants (over 12 months) in this Phase II trial, each implantation will be carried out with the 8 macrobeads per kilogram dosage.

4 INVESTIGATIONAL PLAN

4.1 *Description of Overall Study Design and Plan*

This is an open-label clinical trial. The clinical trial will have duration of approximately 12 months and involve a potential total of four macrobead implants, each no less than three months apart.

Each subject will serve as his own control. This means that changes from baseline to various post-treatment time points will be analyzed for some variables (such as tumor markers, for example). The confidence intervals for these changes will be calculated. Of course, it is not planned for the survival analysis.

Seventy-four (74) male and female subjects with advanced pancreatic cancer or metastatic, treatment-resistant colorectal cancer meeting all the above inclusion criteria will be recruited and treated for the study. Baseline measurements will include tumor burden and size, tumor history and pathological diagnosis and grade, global clinical state, activities of daily living, symptom checklist including tumor-related symptoms, a sense-of-well-being scale, routine clinical biochemistry and any appropriate tumor markers as available, and an assessment of cellular and humoral immune status.

The primary tumor histopathology will be reviewed and will be evaluated with special staining to identify, if possible, the presence or absence of cancer stem cells and niche bodies.

The response of each subject to the intraperitoneal implantation of the RENCA agarose-agarose macrobeads will then be measured over the ensuing 3 months (and a 6, 9, and 12 months, if possible) with respect to changes in:

- Primary tumor size
- Size or number of secondary/metastatic tumors
- Tumor marker or relevant biochemical parameters such as liver enzymes, alkaline phosphatase, lactic dehydrogenase
- Cellular or humoral immune status
- Global clinical status or rating
- Performance status (Karnofsky PS and ECOG PS)
- Activities of daily living (ADL) rating
- Symptom rating/severity (including use of pain medications)
- Quality of life scale
- Circulating tumor cells (when possible)

After each successive implant, follow-up will be at Days 14, 30, 60, and 90. Because much of the testing will be objective in terms of quantifiable clinical laboratory and imaging testing, bias on the part of subjects, investigator, and analysts should be minimized.

Each implant will be considered as Day 0. Post implant follow-up visits will be done in reference to the corresponding implantations i.e. Days 14, 30, 60 and 90 for each implantation.

4.2 Study Device/Biological Product

In this study, the study device/drug is the RENCA macrobead. The cancer cell-containing agarose-agarose macrobeads that are to be used for the Phase II clinical trial are composed of two concentric spherical agarose layers. The inner layer, which is also the layer in which the neoplastic cells (in this case, mouse renal adenocarcinoma cells) are embedded, is made up of 1.0% agarose. The outer layer is composed of 5% agarose. 150,000 mouse renal adenocarcinoma (RENCA) cells are placed in each bead. The diameter of the macrobead is 6,000-8,000 μM or 6-8 mm. Its structure is such that molecules above 80,000 kD are largely excluded from either entering or leaving the bead. Importantly, the cancer cells, although they proliferate in the inner layer of agarose, do not invade the outer layer or escape from an intact bead. In addition, peritoneal or immune system cells from the host cannot enter into the macrobead as well. The macrobeads produce the inhibitory effect for at least 3 years *in vitro* and up to 6 months *in vivo* in animal studies. Data from the Phase I human clinical trial indicate the macrobeads have a functional longevity of from 3 to 4 months.

The cancer-cell containing macrobead is derived from previous and currently ongoing work with a porcine-islet containing agarose-agarose macrobead, an IND for the human Phase I testing of which has been submitted to the FDA (IND # 9672, originally submitted April 9, 2001 and now continuing with further submissions to address the outstanding "clinical hold" issues). This islet macrobead is described in detail in that IND and also in publications from our laboratory (Jain et al, 1995, 1999; Gazda, 2003, Gazda et al, 2005, Vinerean et al, 2008 contained in that IND).

The overall process of preparing the RENCA-cell-containing macrobead is described in the IND documents. As for the islet macrobeads, the cancer macrobeads are placed in the peritoneal cavity in humans. In the peritoneal cavity the beads should remain free (floating) in the intraperitoneal space. They do not become vascularized and thus will remain as implants rather than true grafts.

It is important to emphasize that the macrobeads must be allowed to “mature” *in vitro* prior to their implantation into animals or humans willing to participate in the Phase II trial. Although there is an early proliferation-inhibitory effect related to the apoptotic death of cancer cells in the macrobead, the effect of interest and therapeutic effectiveness is seen after approximately three weeks increasing to a maximum by approximately 8-10 weeks. The appearance of the inhibitory effect coincides with dramatic changes in the tumors cells in the 1% agarose matrix.

The use of immunohistological and gene chip microarray techniques indicates that the cancer cells in the macrobeads undergo dramatic changes over the first several weeks of their encapsulation. After 14-21 days, the cells begin to form ovoid colonies, which are characterized by proliferation (as indicated by a proliferation marker, Ki67) and growth inhibition (as indicated by the appearance of p27, a cyclin-dependent kinase inhibitor, which acts to inhibit cell proliferation at the G1-S checkpoint of the cell cycle). Changes in the expression of genes involved in signal transduction and stem cell pathways are confirmatory of these dramatic changes in the cell populations within the bead. For example, they show decreased expression of genes related to DNA synthesis and angiogenesis (VEGF).

In sum, the colonies formed by the RENCA cells thus emerge following a process marked by both proliferation and apoptotic cell death. The appearance of the cell-proliferation inhibitory effect coincides with the formation of the colonies. It should be emphasized again that RENCA cells removed from the colonies in the macrobeads after periods of up to 3 years return quickly to their prior malignant cell growth patterns both *in vitro* and *in vivo*.

The cellular products of the cancer-cell-containing macrobeads are beginning to be resolved by a variety of techniques including most importantly, the gene arrays already described, as well as Western blot analysis. The products indicating the greatest changes include osteocalcin, bone morphogenic protein-4, GADD45, connexin 43, and aldehyde dehydrogenase. It would appear from the data we have that there are likely to be multiple signals. Based on the physical constraints of the 5% outer layer of agarose, the active product(s) must be less than 80 kD in molecular weight, but may include proteins, peptides, and lipids of many different types. It is possible that small tumor antigens are also released, but it does not appear that these are one and the same with the signaling molecules. A recent advance has been the ability to maintain the macrobeads in serum-free medium. Analyses of the serum-free conditioned media by gel electrophoresis indicate that there are approximately 20 bands. These are being analyzed now to determine which are the signals producing the inhibitory effect on the growth of non-constrained tumor cells.

